### **10.1 Classification of Causality**

Attribution is the relationship between an adverse event or serious adverse event and the study treatment. Attribution will be assigned as follows:

- Definite – The AE is clearly related to the study treatment.
- Probable – The AE is likely related to the study treatment
- Possible – The AE may be related to the study treatment.
- Unlikely - The AE is doubtfully related to the study treatment.
- Unrelated - The AE is clearly NOT related to the study treatment

PROTOCOL NUMBER: CCB-CRISIS-01  
PROTOCOL VERSION DATE: 01MAY2020

Page 38 of 55

### Guidance for assessing causality:

The Investigator will need to determine whether an AE is considered related to (“caused by”) the study drug rather than some underlying condition, for example, COVID-19.

For the purposes of this study, ‘drug related’ shall mean ‘Definite’, ‘Probable’ and ‘Possible’ relationship to drug as determined by the Investigator.

## **10.2 Classification of Severity**

The descriptions and grading scales found in the revised NCI CTCAE version 4.03 will be utilized for AE reporting. All appropriate treatment areas should have access to a copy of the criteria. The CTCAE version 4.03. A copy of the CTCAE version 4.03 can be downloaded from the Cancer Therapy Evaluation Program (CTEP) web site [http://ctep.cancer.gov/protocolDevelopment/electronic\\_applications/ctc.htm](http://ctep.cancer.gov/protocolDevelopment/electronic_applications/ctc.htm).

AEs that are expected are subject to expedited reporting only if the adverse event varies in nature, intensity or frequency from the expected toxicity information that is provided in the Investigator Brochure.

## **10.3 Serious Adverse Event (SAE) Reporting**

The regulatory definition of an SAE is any untoward medical occurrence or effect that at any dose:

- results in death;
- is life threatening (at the time of the event);
- requires in-patient hospitalization or prolongation of existing hospitalization;
- results in persistent or significant disability / incapacity, or
- is a congenital anomaly / birth defect;
- all other events that are considered medically serious by the Investigator.

**Disability** is defined as a substantial disruption of a person’s ability to conduct normal life functions.

**A life-threatening adverse event** is one that places the patient/subject, in the view of the Investigator, at immediate risk of death from the event as it occurred. It does not include an event that, had it occurred in a more severe form, might have caused death.

**An unexpected adverse event** is any adverse drug event, the nature or severity of which is not consistent with the applicable product information (e.g. IB for an unauthorized investigational product or summary of product characteristics for an authorized product).

Enter only one event as the reason for the SAE on the SAE form. Other non-serious events which did not directly result in the SAE should be detailed in the description section on the SAE form and listed separately as AEs if necessary. For fatal SAEs, report the cause of death as an SAE with a fatal outcome rather than reporting death as the SAE term.

Note that hospitalizations for the following reasons should not be reported as SAEs:

PROTOCOL NUMBER: CCB-CRISIS-01  
PROTOCOL VERSION DATE: 01MAY2020

Page 40 of 55

The Sponsor is to ensure that all relevant information about **fatal or life-threatening** SUSARs are appropriately recorded and reported to the concerned Regulatory Authority and to the concerned IRB(s) within seven (7) calendar days of the date of first report to the Medical Monitor/Sponsor. Follow-up information is to be subsequently communicated to the relevant Regulatory Authority within an additional eight calendar days.

All other SUSARs are to be reported to the Regulatory Authority and to the IRB(s) concerned as soon as possible within a maximum of fifteen calendar days of first knowledge by the Medical Monitor/Sponsor.

The Medical Monitor/Sponsor or designee must also inform all Investigators studying the investigational medicinal product about SUSARs and ensure that all IRBs have been notified.

For reported deaths of a subject, the Investigator shall supply the Sponsor and the IRB(s) with requested additional information on an expedited basis.

### **10.5 Pregnancies**

Pregnancy occurring in a female subject or a subject's partner during the study period will be documented in the subject's source documents and reported to the Sponsor Contact and to the IRB by the investigational staff within 1 working day of their knowledge of the event. The collection period for a pregnancy occurring in a subject or a subject's partner will begin at the first dose of study drug and will continue through 90 days after the last dose of study drug. Monitoring of the subject or partner should continue until the conclusion of the pregnancy, if the subject or subject's partner has consented to this. Monitoring of the baby should continue for 3 months after birth, if the subject or subject's partner has consented to this.

Pregnancy itself is not an AE; it should be reported for tracking purposes. The Investigator or designee will discontinue the pregnant subject from the treatment aspects of the study, continue to follow her per protocol for safety outcomes only, and advise her to seek prenatal care and counseling from her primary care provider. Data on fetal outcome and breast-feeding will be collected for regulatory reporting and drug safety evaluation.

If the pregnancy is due to a subject's failure to comply with the contraceptive requirements of this protocol, this should also be documented as a protocol deviation.

Complications of pregnancy or congenital abnormalities in the newborn child will be reported appropriately as AEs.

The site clinical staff will request the pregnant subject to notify the site of the outcome of the pregnancy (i.e., birth, loss, or termination). To help ensure this, the site clinical staff will follow-up with the subject until the end of pregnancy, with the subject's consent. This request and the subject's response will be documented in the subject's source document.

### **10.6 Safety Monitoring for Hematologic Toxicities**

Myelosuppression is a known effect of DHODH inhibition that is associated with prolonged exposure and high doses. To reduce the risk of this effect with brequinar in COVID-19 subjects, the extensive brequinar safety database with over 1,000 patients has been evaluated to select a dose

PROTOCOL NUMBER: CCB-CRISIS-01  
PROTOCOL VERSION DATE: 01MAY2020

Page 41 of 55

level expected to be safe and well tolerated with regard to hematologic toxicity. In addition to enhancing safety by selecting a relatively brief 5-day exposure and a low brequinar dose, all subjects in the clinical trial will initially be hospitalized as in-patients and will be under the care of highly qualified infectious disease, critical care, and associated medical personnel. As is standard of care for moderately to severely ill in-patients, daily samples will be obtained for hematology assessments including complete blood count with full differential (WBC, RBC, hemoglobin, hematocrit, platelet count, absolute neutrophils, absolute lymphocytes, absolute monocytes, absolute eosinophils, and absolute basophils). Any clinically significant out-of-range laboratory values will be assessed by hospital staff in a timely manner and treatment needs addressed as appropriate. Clinically significant out-of-range laboratory results will be reported as adverse events.

In addition to real time assessments by the treating clinical team, the Clear Creek Medical Monitor will assess the available hematology data on a weekly basis to identify any pathologic trends or safety issues. Any apparent increase in the expected rate or severity of hematologic safety events will be discussed with the Principal Investigators, the Sponsor, and the Medical Monitor. In addition, the Data Safety Monitoring Board will assess available hematology data on a periodic basis to independently assess any pathologic trends or safety issues. If the rate or severity of hematologic toxicities appears to be above the expected rate or the severity appears worse than that expected, the trial enrollment will be suspended and no further subjects will be treated while a comprehensive data review is conducted. Depending on the outcome of the safety review the study may be stopped, the design adjusted, or the study may continue as designed.

Subjects who are discharged from the hospital before Day 7 will have follow up contacts with study staff (phone calls or other digital media) on Days 7, 15 and 29. Early discharge subjects in the brequinar treatment group will also have samples for safety labs (hematology and chemistry) obtained either at the research facility or at an outpatient laboratory on Study Days  $7 \pm 2$  and  $15 \pm 2$ . The safety laboratory results are to be initially assessed in real time by the Principal Investigator or designated person and the Medical Monitor. Any study drug-related clinically significant out-of-range laboratories or study drug-related adverse events will be followed as needed until resolution or stable.

The in-hospital assessments and phone call visits will specifically ask about possible hematologic toxicity including any evidence of the list below. Early discharge subjects will be provided with a list of the following events in lay terms and will be instructed to call the research team if any of these events occur.

- Ecchymosis/purpura/petechiae
- Epistaxis
- Hemoptysis
- Hematuria
- Gingival bleeding
- Prolonged bleeding time from needle sticks, abrasions or lacerations
- Hematemesis
- Rectal bleeding
- Blood in stool

PROTOCOL NUMBER: CCB-CRISIS-01  
PROTOCOL VERSION DATE: 01MAY2020

Page 42 of 55

- Any other unusual bleeding noted by the subject or caregiver

Any of these symptoms considered clinically significant will be recorded as an adverse event and must be followed until resolved or stable.

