## **6 TRIAL ENDPOINTS**

### **6.1 Primary Endpoint**

- Safety/tolerability measured by rates of post randomization adverse events and hematology/chemistry safety labs.

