## 10 ADVERSE EVENT REPORTING

An adverse event is any untoward medical occurrence in a patient or clinical trial subject administered a medicinal product and which does not necessarily have a causal relationship with this treatment. An AE can therefore be any unfavorable and unintended sign (including an abnormal laboratory finding), symptom, or disease temporally associated with the use of the medicinal product, **whether or not considered related to the medicinal product.**

Events that occur prior to informed consent will be entered as medical history; AEs that occur after informed consent will be entered on the AE form.

Subjects will be questioned and observed for evidence of AEs, whether or not judged by the Investigator or designated person to be related to study drug. All AEs will be documented in the subject's medical record and CRF. For any pre-existing condition or abnormal laboratory finding that changes in severity after dosing, this change should be recorded as an AE. New abnormal laboratory findings that are clinically significant are considered AEs.

All adverse events will be collected from the time of informed consent through Day 15. After Day 15, collect/record only Serious Adverse Events (SAEs) or those judged by the Investigator or designated person to be related to study drug. AE details are to be documented including start and stop date and times, whether continuous or intermittent, severity, any intervention utilized to correct the event (e.g., medication, surgery, or other therapy), outcome and the relationship to the study drug.

AEs identified in the protocol as critical to the evaluation of safety must be reported to the Sponsor by the Investigator according to the reporting requirements within the time periods specified in the protocol.

AEs determined by the Investigator to be related to study drug must be followed until resolution or until they are considered stable or for at least 30 days after discontinuation of study drug.

Any serious adverse events (SAEs) experienced after 30 days post the last dose of study drug should only be reported to the sponsor if the investigator suspects a causal relationship to the study drug.

Abnormal laboratory values or test results occurring after study enrollment constitute AEs only if they induce clinical signs or symptoms, are considered clinically significant, or require therapy.

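### Section 10.6 ties recording of the solicited bleeding signs to an undefined clinical-significance test that Section 10 keeps for laboratory and test results, so mild signs can be left out of the adverse-event part of the primary endpoint

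*Protocol*

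**What the plan says.** All references are to the protocol version dated 01 May 2020.

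- **Definition (Section 10).** "An AE can therefore be any unfavorable and unintended sign (including an abnormal laboratory finding), symptom, or disease". No severity or significance threshold is attached to signs or symptoms.
- **Recording (Section 10).** "All AEs will be documented in the subject's medical record and CRF". On timing: "All adverse events will be collected from the time of informed consent through Day 15". After Day 15 only serious or study drug-related events are collected.
- **Where Section 10 filters.** Abnormal laboratory values and test results "constitute AEs only if they induce clinical signs or symptoms, are considered clinically significant, or require therapy". The condition is confined to those findings.
- **Solicitation (Section 10.6).** "The in-hospital assessments and phone call visits will specifically ask about possible hematologic toxicity including any evidence of the list below". The list includes petechiae, epistaxis, gingival bleeding, hematuria and prolonged bleeding.
- **Recording of the solicited signs (Section 10.6).** "Any of these symptoms considered clinically significant will be recorded as an adverse event and must be followed until resolved or stable".
- **Primary endpoint (Section 6.1).** "Safety/tolerability measured by rates of post randomization adverse events"; the sentence goes on to add the hematology and chemistry safety laboratory results.
- **Analysis (Sections 10.2 and 11.2).** AEs are graded by CTCAE v4.03 and tabulated by severity. All laboratory results are summarized, without a significance filter.

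**The concern.** Petechiae or a nosebleed is a sign or symptom, not a laboratory value. Under Section 10 it is an AE whatever its grade. Under Section 10.6 its entry as an AE hangs on a judgement for which no criterion is given, made by staff who know the treatment arm. Two sites can each follow the protocol and count the same subject differently: one lists a Grade 1 epistaxis, the other lists nothing. A mild headache, which is not on the list, would be recorded at both.

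This matters because AE rates are one of the two components of the primary endpoint and myelosuppression, in particular thrombocytopenia, is a main expected toxicity of brequinar (Sections 3.7 and 10.6). Grading by CTCAE and tabulating by severity presuppose that mild events reach the database. With about 16 treated subjects, one or two unrecorded subjects change the descriptive picture.

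**Working it through.** **1. The two rules side by side**

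| Finding | Section 10 | Section 10.6 |
|---|---|---|
| Laboratory or test result | AE if it causes signs or symptoms, is clinically significant, or needs therapy | Clinically significant results are AEs |
| Sign or symptom on the bleeding list | AE, no threshold | Stated to be recorded if considered clinically significant; nothing said about the rest |
| Any other sign or symptom | AE, no threshold | Not addressed |

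On laboratory values the sections are compatible; Section 10.6 says "Clinically significant out-of-range laboratory results will be reported as adverse events". They diverge in the second row only. If Section 10 governs, the qualifier in Section 10.6 does nothing to recording. If Section 10.6 governs as the specific rule, mild listed signs are not entered. Either way the text needs correction.

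**2. What can be computed**

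The protocol states no figure for this point, so there is none to reproduce. The planned 24 subjects at 1:2 give 24/3 = 8 on standard of care and 24 × 2/3 = 16 on brequinar (Section 7.1). The rest is illustration on assumed inputs: p is the true proportion of subjects with any listed sign, and f is the share of those subjects with a sign judged clinically significant. Neither is in the documents.

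Expected recorded count = n × p × f. Probability of at least one recorded = 1 − (1 − p × f)^n. For n = 16, each cell gives count and probability:

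| p (assumed) | f = 1 (all recorded) | f = 0.5 | f = 0.25 |
|---|---|---|---|
| 10% | 1.6; 0.82 | 0.8; 0.56 | 0.4; 0.33 |
| 20% | 3.2; 0.97 | 1.6; 0.82 | 0.8; 0.56 |
| 30% | 4.8; 0.997 | 2.4; 0.93 | 1.2; 0.71 |

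For example, at p = 20% and f = 0.5: 16 × 0.20 × 0.5 = 1.6, and 1 − 0.90^16 = 0.82.

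The nearest figure in the protocol is one case of mild thrombocytopenia in 39 subjects given 100 mg/day or less for 5 days (Section 3.6.2). That is not a rate of bleeding signs in COVID-19. If 1/39 = 2.6% were used for p, the expected count would be 16/39 = 0.41 with all recorded and 0.21 at f = 0.5. The size of the effect therefore follows the assumption.

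**3. Direction between arms**

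Writing B for brequinar and S for standard of care, the recorded difference is p_B × f_B − p_S × f_S. The questioning in Section 10.6 is not limited to brequinar subjects, so f acts in both arms. Take equal true rates of 20%. With f_B = 0.25 and f_S = 0.5 the recorded rates are 5% and 10%; with the shares exchanged they are 10% and 5%. Open-label judgement could push either way, and the documents do not settle which.

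**The case against.** The strongest reply is that nothing is lost. Section 10.6 never says that other signs go unrecorded; a reader might infer an only-if rule, but those words are absent. The general duty to document all AEs is not amended, and the sentence can be read as extending follow-up until resolved or stable to significant bleeding signs whatever their cause, since Section 10 requires such follow-up only for drug-related AEs. The first part stands: the text shows an unresolved conflict, not a certain loss. The second does not remove the conflict, because the same condition also governs recording as an AE.

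Three further objections stand.

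- **Laboratory component.** The primary endpoint also includes the safety laboratory results, and Section 11.2 summarizes all of them, so falls in platelets stay in the endpoint. This protection is partial: platelet counts do not measure bleeding, and Appendix A does not treat samples missed at phone visits as deviations.
- **Monitoring.** A reader might infer that the Medical Monitor and the data safety monitoring board would lose their early warning. Section 10.6 describes both as reviewing available hematology data and does not say that either relies on bleeding AE entries.
- **Prior data.** The drug-related events that Section 8.2.1 lists for the 39 low-dose subjects in the three intravenous studies include no bleeding event. That gives no support for assuming a high rate, though those subjects did not have COVID-19.

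**Conclusion.** The conflict is real and specific. Section 10.6 applies to the solicited bleeding signs a clinical-significance condition that Section 10 keeps for laboratory and test results, without defining it and without a rule for the signs that fail it. Where a site follows Section 10.6, mild bleeding signs can be left out of the AE-rate component of the primary endpoint, in either arm.

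Two stronger conclusions are tempting and not supported. One is that mild bleeding drops out of the primary endpoint altogether: the effect reaches the AE-rate component only, and only where Section 10.6 is taken as the operative rule. The other is that brequinar toxicity is understated relative to standard of care by a stated percentage: the condition applies to both arms and no input for the calculation is in the documents. The counts above show only that, with about 16 treated subjects, the choice of rule could alter the descriptive result if such signs are not rare.

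This rests on the 01 May 2020 text. The table of contents lists five later versions, from June to September 2020, in which hematologic monitoring is numbered 10.8; their text is not shown, so whether the sentence persists is unknown.

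**What to change.** Reconcile the passages by replacing the recording rule in Section 10.6 with:

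> Any of these signs or symptoms will be recorded as an adverse event with its CTCAE grade, whether or not considered clinically significant, within the Section 10 collection window (informed consent through Day 15; thereafter SAEs or study drug-related events).

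Leave the existing follow-up requirement as it is, as a separate sentence, and reserve the clinical-significance condition on recording for laboratory and test results, as in Section 10. Stating the collection window keeps the new sentence from conflicting with Section 10; the analysis can still restrict the endpoint to events with onset after randomization.

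The cost is one sentence and a few more Grade 1 AE entries. Before amending, check whether the sentence survives in the later protocol versions.

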### **10.7 Data Safety Monitoring Board**

A Data and Safety Monitoring Board (DSMB) will be established to provide independent oversight to this trial. The primary responsibility of the DSMB will be to review the progress and conduct of the trial in order to maintain scientific rigor and to ensure the wellbeing of subjects participating in the trial. The specific responsibilities of the DSMB will be detailed in a separate DSMB charter. The DSMB will include at a minimum at least one statistician and two clinicians who will perform periodic data review to assess whether there are clinically significant differences between treatment arms that could affect participant safety. Following such a review, the DSMB Chair will advise the Sponsor that the study be stopped, the design changed, or that the study may continue per protocol.

PROTOCOL NUMBER: CCB-CRISIS-01  
PROTOCOL VERSION DATE: 01MAY2020

Page 43 of 55

## **11 STATISTICAL CONSIDERATIONS**

A separate, detailed statistical analysis plan (SAP) will be finalized prior to locking the database. All analyses will be descriptive in nature and presented by group.

Summaries for quantitative variables will include the mean, median, quartiles, standard error, minimum, and maximum. For qualitative variables, the summaries will include the number and percentage of subjects for each outcome, and 95% confidence interval (CI), when appropriate. Any statistical testing will be considered exploratory and descriptive. All computations will be performed using SAS® (Version 9.4 or higher).

Subject disposition, subject demographics and baseline characteristics will be summarized. Subject data listings will also be provided. The following sections will briefly summarize of the planned statistical analyses and analysis sets for the primary and secondary endpoints.

### **11.1 Study Populations for Analysis**

All analyses will be based on the ITT population, which is defined as all randomized subjects.

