
Sample Size:
	
Approximately 24 subjects will be randomized to either standard of care or standard of care plus brequinar in a 1:2 ratio (approximately 8 assigned to standard of care and 16 subjects on brequinar).

Number of Sites:
	
1 - 8

Study Period:
	
An enrollment period of 3 months is expected.

Inclusion Criteria:
	
 
1. Willing and able to provide informed consent for the trial, written, electronic, verbal or other method deemed acceptable by the institution and IRB.
 
2. 18 years of age or older and at least one of the following co-morbidities by subject history or present in the institution’s electronic health record: hypertension, diabetes, chronic kidney disease, chronic obstructive pulmonary disease (COPD) or asthma, cardiovascular disease (coronary artery disease or congestive heart failure), liver cirrhosis, age > 65, BMI > 30.
 
3. If discharged from the hospital prior to Study Day 15 or if follow up is needed for study drug-related adverse event, willing to go to an outpatient laboratory for a laboratory sample as well as a contact (phone call or other digital media) on Study Days 7 and 15 and contact only on Day 29.
 
4. Laboratory-confirmed SARS-CoV-2 infection as determined by real time polymerase chain reaction (RT-PCR) or other FDA-cleared commercial or public health assay.
 
5. Life expectancy > 48h in the opinion of the investigator.
 
6. Hospitalized (in patient with expected duration ≥ 24 hours)
 
7. The effects of brequinar on the developing human fetus are unknown. For this reason, women of child-bearing potential and men must agree to use adequate contraception (hormonal or barrier method of birth control; abstinence) prior to study entry and for the duration of study participation. Should a woman become pregnant or suspect she is pregnant while she or her partner is participating in this study, she should inform her treating physician immediately. Men treated or enrolled on this protocol must also agree to use adequate contraception for the duration of study participation, and for 90 days after completion of brequinar administration.
 

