## **4 TRIAL OBJECTIVES**

### **4.1 Primary Objective**

- To determine the safety and tolerability of standard of care (SOC and SOC plus brequinar in hospitalized COVID-19 subjects.

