### Days 1 - 7 (8 AM ± 8 hours)

- If Day 1 is different date from Screening, confirm subject continues to meet all inclusion and no exclusion criteria.
- Randomize the subject (record date and time of randomization).
- Review Progress Notes and medication records to collect any new or changes to ongoing adverse events or new or changed concomitant medications since previous visit (may be omitted on Day 1 if Screening visit was conducted on same day as Study Day 1). Repeat on Day 7.
- Collect SOC hematology/chemistry results from the EHR on Day 1 (pre-dose) and Day 7 (may be omitted for Day 1 if Screening visit conducted on same date as Study Day 1). Ensure that Day 1 samples are obtained prior to first dose of study drug, if applicable.
- Days 1 (pre-dose), 3, 5, 7:
  - Collect NEWS2 Assessments from the EHR.
  - Collect results for inflammatory markers from EHR for those analyzed locally; collect, process and ship samples for DHO/brequinar PK and cytokine panel to be analyzed at the central laboratory per the Laboratory Manual.
  - Collect and process SARS-CoV-2 nasopharyngeal viral load samples.
  - Record hospitalization status (hospitalized, hospitalized in ICU, discharged) (Day 1 already recorded as part of Inclusion criteria, do not record again).
- Dispense study medication (Days 1 through 5 if in brequinar group) and record date and time of brequinar administration. Keep the drug administration interval as close as possible to 24h. Ensure Day 1 labs are drawn prior to first brequinar dose on Day 1. If a subject taking brequinar is discharged prior to Day 5, administer final dose on day of discharge. Do not give subject study drug to take home.

PROTOCOL NUMBER: CCB-CRISIS-01  
PROTOCOL VERSION DATE: 01MAY2020

Page 34 of 55

- Drug accountability Day 7  $\pm$  2 days.

**Final Visit Day 15** (8 AM  $\pm$  2 days) or Hospital Discharge Day if earlier than Day 15

- Review Progress Notes and the medication record to collect information for any adverse events or new concomitant medications since Day 7 (from EHR if subject still hospitalized, otherwise by phone or other digital media).
- Collect results for SOC hematology/chemistry from the EHR if subject still hospitalized.
- Collect inflammatory markers from EHR for those analyzed locally; collect samples for DHO and cytokine panel to be analyzed at the central laboratory if subject still hospitalized.
- Collect NEWS2 Assessments from the EHR.
- Collect nasopharyngeal viral load sample.

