### **11.4 DHO and Brequinar Concentration Levels**

DHO and brequinar concentrations levels will be summarized using descriptive statistics.

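### Section 11.1 puts the primary safety analysis on all randomised subjects, so any never-dosed brequinar subject would count as exposed; a treated safety set is needed for 11.2

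*Protocol*

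**What the plan says.** All references are to protocol version 01MAY2020 unless stated.

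- Section 11.1 sets one population for everything: "All analyses will be based on the ITT population, which is defined as all randomized subjects". Section 11.2 (safety) adds no other set.
- Section 4.1 makes safety the primary objective, and Section 6.1 defines the primary endpoint: "Safety/tolerability measured by rates of post randomization adverse events and hematology/chemistry safety labs".
- Section 11 says "All analyses will be descriptive in nature and presented by group" and, for qualitative variables, that "the summaries will include the number and percentage of subjects for each outcome, and 95% confidence interval (CI), when appropriate". No interval method is given.
- The Synopsis plans "approximately 8 assigned to standard of care and 16 subjects on brequinar".
- The Synopsis asks for the first brequinar dose as soon as possible after randomisation, and Section 9.5 makes it depend on pharmacy staff. The Synopsis counts an adverse event as post-randomisation from the date and time of randomisation, not from first dose.
- Section 8.7.5 requires records that show who received study drug, and Section 9.5 requires the date and time of each brequinar administration.

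**The concern.** For the brequinar arm, a safety study asks how often harm occurs in people who took the drug. An all-randomised denominator answers a slightly different question once anyone in that arm is not dosed, because such a subject cannot have a drug-caused event but still enlarges the denominator.

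The design leaves room for this. The trial is open label, randomisation comes before the first dose, and subjects may withdraw at any time. Section 7.1 enrols until about 24 subjects have completed, and Section 8.4 defines completion by assessments through Day 15, not by dosing. An undosed subject with telephone follow-up could therefore fill a brequinar place without being replaced.

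This is not a detail left to the statistical analysis plan. Section 11.1 covers all analyses, so a plan that used a treated set for the main safety table would depart from the protocol. At stake are the toxicity rates and upper limits reported for an arm of about 16.

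**Working it through.** **Inputs.** 24 subjects at 1:2 (Synopsis; Section 7.1). 95% intervals where appropriate (Section 11). The interval method is not stated, so the exact Clopper-Pearson interval is assumed. The number never dosed is not in the documents and is assumed to be 0, 1, 2 or 4 of 16.

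**Step 1, the plan's own figure.** 24 × 1/3 = 8 on standard of care and 24 × 2/3 = 16 on brequinar. This reproduces the stated split. The protocol gives no sample size, power or precision calculation to reproduce.

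**Step 2, toxicity with no observed events.** The upper limit of the exact two-sided 95% interval for 0 of n is 1 − 0.025^(1/n).

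| Undosed of 16 | Dosed n | Upper limit, dosed | Upper limit, all 16 randomised | Difference (points) |
|---|---|---|---|---|
| 0 | 16 | 20.6% | 20.6% | 0 |
| 1 | 15 | 21.8% | 20.6% | 1.2 |
| 2 | 14 | 23.2% | 20.6% | 2.6 |
| 4 | 12 | 26.5% | 20.6% | 5.9 |

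**Step 3, toxicity with events.** If all events occur in dosed subjects, the rate in the dosed is the all-randomised rate times 16/n: 16/15 = 1.07, 16/14 = 1.14, 16/12 = 1.33. With 2 events, the rate is 2/16 = 12.5% (upper limit 38.3%) on all randomised. It is 2/15 = 13.3% (40.5%), 2/14 = 14.3% (42.8%) or 2/12 = 16.7% (48.4%) on the dosed.

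**Step 4, undosed subjects replaced.** If enrolment continued until 16 were dosed and 18 had been randomised to brequinar, zero events would give an upper limit of 18.5% on all randomised against 20.6% on the dosed.

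**Step 5, the opposite direction.** Suppose one subject is undosed and has an adverse event after randomisation, and the other 15 have none. All randomised gives 1/16 = 6.25% (upper limit 30.2%); the dosed set gives 0/15 = 0% (upper limit 21.8%). For all-cause events the all-randomised rate can therefore be too high as well as too low.

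**The case against.** The strongest reply is that the effect is conditional and probably small. No passage gives an expected number undosed. Subjects are inpatients with an expected stay of at least 24 hours, the first dose is to follow randomisation as soon as possible, and capsules are held at the institution. If everyone is dosed, the two sets are the same. With one or two undosed, the zero-event limit moves by about 1 to 3 points, in a descriptive trial with no stated threshold that turns on such a shift. Section 11.2 also tabulates events by relationship to treatment and lists every event, so a reader with the dosing records could identify an undosed subject. The all-randomised set also preserves the comparison between arms. All of this stands. It limits the size of the point but does not justify the rule as the only basis for the primary analysis.

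Four stronger readings might be inferred, and the documents do not support them.

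- *That toxicity rates are understated.* This needs at least one undosed brequinar subject, and Step 5 shows that all-cause rates can move the other way.
- *That early discharge makes the problem worse.* Section 8.4 has a subject discharged before Day 5 take a final dose that day, and Section 9.5 adds "Do not give subject study drug to take home". Short courses are therefore part of the planned regimen. Subjects with 1 to 4 doses have received the drug and belong to a treated set too, so the denominator is unchanged. Section 11.1 says who is analysed, not that each had full exposure.
- *That the concentration summaries are spoiled.* Section 11.4 says "DHO and brequinar concentrations levels will be summarized using descriptive statistics". Missing values do not enter means, medians or quartiles, so undosed subjects without samples do not alter them.
- *That the rule governed the final trial.* The versions of 31MAR2020 and 10APR2020 carry the same sentence, but Section 11.1 of the versions from 05JUN2020 to 10SEP2020 is not shown.

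**Conclusion.** The point holds in conditional form. Version 01MAY2020 fixes the primary safety analysis on all randomised subjects and provides no treated set. If any brequinar subject is never dosed, drug-caused toxicity rates and their upper limits can be understated, and all-cause event rates can be distorted either way.

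The size depends wholly on an assumed number undosed and on exact intervals in an arm of 16. The zero-event upper limit is unchanged with none undosed, and rises by 1.2, 2.6 or 5.9 points with one, two or four. Four of 16 is an illustrative extreme with no basis in the documents. The correction is worth making because safety is the primary endpoint, the rule is explicit, and the data needed to form a treated set are already collected.

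**What to change.** In Section 11.1, define a safety set analysed by treatment received: subjects with at least one brequinar dose, against subjects randomised to standard of care who received none. Use it for the main safety table in Section 11.2. Keep all randomised subjects for the efficacy analyses in Section 11.3, and as a supportive safety table that preserves the randomised comparison. Report the number randomised to brequinar and never dosed, so that a reader can see whether the two tables can differ.

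A table by number of doses received is optional; it is not a reason for the change. If later versions kept the sentence in Section 11.1, the same edit applies there.

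The cost is one definition and one extra table, with no new data. Limits become slightly wider if anyone is undosed. In that case the treated comparison is also no longer strictly randomised, for example if a subject deteriorates before the first dose. That is why the all-randomised table should stay.
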